5.2 RATIONALE

Two previous clinical studies of omiganan in rosacea were conducted. CLS001-R-001 was a double-blind, multicenter, randomized, vehicle-controlled, parallel group study in 240 adult subjects with subtype 2 papulopustular rosacea. Subjects were treated for 9 weeks. The primary objective of the study was to evaluate the safety and efficacy of omiganan pentahydrochloride topical gel 1% w/w and 2.5% w/w compared to vehicle gel in subjects with papulopustular rosacea. Eligible subjects were randomized to 5 treatment groups in a 2:2:2:1:1 ratio. The treatment arms were:

- Omiganan pentahydrochloride topical gel, 1% w/w QD
- Omiganan pentahydrochloride topical gel, 2.5% w/w QD
- Omiganan pentahydrochloride topical gel, 2.5% w/w BID
- Vehicle QD
- Vehicle BID

All efficacy variables improved compared with Baseline in all treatment groups in the modified intent to treat (MITT) analysis. The reductions from Baseline tended to be greatest in the omiganan 2.5% QD group; however, there were no statistically significant differences between the active treatment groups and the combined vehicle group for any efficacy variable at the Week 9/end of treatment endpoint for the MITT population.

CONFIDENTIAL

Version Date: 10 July 2015

Analyses of the per protocol (PP) population were supportive of the results for the MITT population. All efficacy variables improved relative to Baseline for all treatments. For the Week 9 analyses, there were statistically significant differences between active and vehicle treatment for change from Baseline in inflammatory lesion count (for omiganan 2.5% QD versus vehicle, in favor of omiganan) and for scaling/peeling (omiganan 2.5% BID versus vehicle, in favor of vehicle).

Further exploratory analyses with comparisons of the treatment groups, stratified by Baseline lesion count, demonstrated statistically significant difference in the mean change from baseline in inflammatory lesions counts for omiganan 2.5% QD versus vehicle QD in subgroups with more severe rosacea (> 14.5 lesions at baseline). Overall in the MITT population (all subjects), the mean change from Baseline in lesion count at Week 9 for omiganan 2.5% QD and vehicle QD was -5.93 versus -1.50, respectively ($P=0.041$). For subjects with a baseline lesion count >14.5, the mean change in lesion count was -7.58 and +0.63 for 2.5% QD and vehicle QD, respectively ($P=0.013$) at Week 9.

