7.5.6 Adverse Event

7.5.6.1 Definition of Adverse Event

An adverse event (AE) is any unfavorable and unintended sign (including a clinically significant abnormal laboratory finding, for example), symptom, or disease temporally associated with the use of a medicinal product, whether or not considered related to the medicinal product. Clinical signs and symptoms of rosacea: erythema, telangiectasia, burning, dryness, scaling/peeling and pruritus are considered as part of the baseline dermatological history. If a new rosacea sign or symptom or worsening of a rosacea sign or symptom is believed by the investigator to be related to the study drug and not the disease, then it should also be recorded as an AE.

At each visit, the study site personnel will question the subject about adverse events using an open question taking care not to influence the subject's answers, e.g., "Have you had any problems since your last visit?"

Any adverse event, whether or not it is related to the test products, will be reported on the source document and eCRF along with the date of onset, the severity, the relationship to the test product and the outcome. Under certain circumstances, additional information may be requested.

When an adverse event persists at the end of the study, the Investigator will ensure a follow-up of the subject until the Investigator/CRO/Sponsor agree that the event is satisfactorily resolved or that no further follow-up is required.

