### **5.3 Efficacy Endpoints**

The co-primary endpoints are:

- The absolute change from baseline to Week 12 in inflammatory lesions (papules and pustules).
- IGA at Week 12: 2 point reduction; Clear or Almost Clear (IGA 0, 1).

Secondary endpoints are:

- The absolute change from baseline to Week 9 in inflammatory lesions (papules and pustules).
- The absolute change from baseline to Week 6 in inflammatory lesions (papules and pustules).
- IGA at Week 9: 2 point reduction; Clear or Almost Clear (IGA 0, 1).
- IGA at Week 6: 2 point reduction; Clear or Almost Clear (IGA 0, 1).

Exploratory endpoints:

- The absolute change from baseline to Weeks 1 and 3 in inflammatory lesions (papules and pustules).
- Percentage of subjects with an IGA of clear or almost clear (0 or 1) at Weeks 1 and 3.
- Percentage of subjects with a 2 point IGA reduction at Weeks 1 and 3.
- Percentage of subjects with an Investigators Assessment of Erythema (IAE) of clear or almost clear (0 or 1) at each visit.
- Percentage of subjects with telangiectasia score of none or mild (0 or 1) at each visit.
- Percentage of subjects with scaling/peeling score of none or mild (0 or 1) at each visit.
- Percentage of subjects with pruritus score of none or mild (0 or 1) at each visit.

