#### **5.4.5 Week 16 (4 Week Follow-Up) Summary**

Summary statistics for Week 16 study period will include baseline demographics, disposition, exposure, safety, and efficacy variables.

Efficacy summaries will include:

- The absolute change from baseline to Week 16 in inflammatory lesions (papules and pustules).
- IGA at Weeks 16: 2 point reduction; Clear or Almost Clear (IGA 0, 1).
- Percentage of subjects with an Investigator Assessment of Erythema (IAE) of clear or almost clear (0 or 1) at Week 16.
- Percentage of subjects with telangiectasia score of none or mild (0 or 1) at Week 16.
- Percentage of subjects with scaling/peeling score of none or mild (0 or 1) at Week 16.
- Percentage of subjects with pruritus score of none or mild (0 or 1) at Week 16.

Safety summaries will include:

- concomitant medications
- adverse events that were emergent during the follow-up study period
- vital signs and laboratory tests.

All Week 16 summaries will be performed by original double-blind randomized treatment group, and overall.

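### The planned percent-at-0-or-1 analysis misses part of the worsening in local skin signs, and all erythema worsening from an eligible baseline, and no safety table fills the gap

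*SAP*

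**What the plan says.** Protocol 7.4.2 and 7.4.3 grade erythema from 0 to 4, and telangiectasia, scaling/peeling and pruritus from 0 to 3, at Screening and every later visit.

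The planned analyses are all exploratory efficacy endpoints in SAP 5.3. For erythema the entry is "Percentage of subjects with an Investigators Assessment of Erythema (IAE) of clear or almost clear (0 or 1) at each visit". For scaling/peeling it is "Percentage of subjects with scaling/peeling score of none or mild (0 or 1) at each visit", and the entries for telangiectasia and pruritus take the same form with the same cut.

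SAP 5.4.5 repeats the same cut for the follow-up visit, for example "Percentage of subjects with scaling/peeling score of none or mild (0 or 1) at Week 16". Protocol 7.7.6.3 and 7.7.13 match. Neither document plans a shift table, a change from baseline or a count of worsened subjects for these scales.

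On adverse events, Protocol 7.5.6.1 gives a general definition that applies "whether or not considered related to the medicinal product". It then treats erythema, telangiectasia, burning, dryness, scaling/peeling and pruritus as baseline history, and directs recording where a new sign or "worsening of a rosacea sign or symptom is believed by the investigator to be related to the study drug and not the disease". Sections 7.4.2 and 7.4.3 carry the same attribution condition.

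SAP 5.4.4 covers adverse events, vital signs and laboratory values. Protocol 7.7.12 also plans shifts in physical examinations, and the limited examination in 7.5.2 includes skin. SAP 5.4.4 does not carry these shifts forward, and SAP 7.0 does not list their removal.

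**The concern.** Local tolerability is a central safety question for a gel left on the face every day. A measure that merges none with mild, and moderate with severe, describes how many subjects look acceptable at a visit. It does not describe how many got worse. Grade 1 scaling is a visible sign (cracking that is easy to see), yet a subject who goes from no scaling to grade 1 still counts as favourable.

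Adverse-event reporting would normally act as the safety net. Here the signs in question are also signs of the disease under treatment, and the protocol ties their recording to the investigator's view of cause. A blinded investigator can reasonably put irritation down to rosacea, and sites may apply the two statements in 7.5.6.1 differently. Burning and dryness have no scale, so adverse events are the only specific route for them.

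The sponsor's first Phase 2 study shows that the sign is relevant. Protocol 5.2 reports a statistically significant per-protocol difference at Week 9 in "scaling/peeling (omiganan 2.5% BID versus vehicle, in favor of vehicle".

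At stake is whether the report can say how many subjects in each arm had worse skin signs on treatment, independently of attribution.

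**Working it through.** The plan states no figure on this point, so there is none to reproduce. The check counts which worsening moves the planned endpoint can register, then gives one illustration.

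**1. Moves on each scale.** A scale from 0 to K has K(K+1)/2 possible worsening moves. A move is invisible to the endpoint if both grades lie on the same side of the cut (0-1 versus 2 and above).

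| Scale and starting grades | Worsening moves | Invisible | Which |
|---|---|---|---|
| Scaling/peeling, pruritus (0-3, no entry minimum) | 3×4/2 = 6 | 2 | 0→1, 2→3 |
| Telangiectasia (0-3; inclusion criterion 4 requires it present, so start is 1 or more) | 3 | 1 | 2→3 |
| IAE (0-4), any start | 4×5/2 = 10 | 4 | 0→1, 2→3, 2→4, 3→4 |
| IAE from an eligible baseline (2 or more, inclusion criterion 5) | 3 | 3 | 2→3, 2→4, 3→4 |

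On the full 0-3 scale, 2 of the 3 one-grade moves are invisible. The visible moves enter only a net percentage at each visit, where improvers can offset them.

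**2. Illustration for scaling or pruritus.** All rates here are assumed; the documents give none. Suppose 60% of subjects start at grade 0, and 25% of these on omiganan and 10% on vehicle worsen to grade 1.

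- Any worsening: 0.60 × 0.25 = 15% versus 0.60 × 0.10 = 6%, a difference of 9 points.
- Planned endpoint: a difference of 0, because every assumed worsening stops at grade 1.
- If 40% start at grade 0: 10% versus 4%, 6 points hidden. If 80% start at 0: 20% versus 8%, 12 points hidden.
- If instead a share s of the worseners in each arm reached grade 2 or 3, the planned endpoint would show 9 × s points: 3 points for s = 1/3, and all 9 for s = 1.

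**3. Precision.** Normal approximation, two-sided 0.05: power = Φ[(d − 1.96·se0)/se1], with d = 0.09, se0 = √(2 × 0.105 × 0.895/n) and se1 = √((0.15 × 0.85 + 0.06 × 0.94)/n).

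- n = 60 per arm: se0 = 0.0560, se1 = 0.0554; (0.09 − 0.1097)/0.0554 = −0.36; power about 36% (25% to 47% over the 40-80% range).
- n = 225 per arm: se0 = 0.0289, se1 = 0.0286; (0.09 − 0.0566)/0.0286 = 1.17; power about 88% (70% to 96%).
- The 95% interval, 9 ± 1.96·se1, is about −2 to 20 points at 60 per arm, and 3.4 to 14.6 at 225.

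Sixty per group is the planned interim size (SAP 5.4.3), and 225 is the planned full size. SAP 5.4.2 and 7.0 say enrolment was discontinued after the interim analysis. The final number per arm is not stated.

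**4. Other routes to a safety table.** SAP 5.4.4 has none for these scales. The physical-examination shifts in Protocol 7.7.12 would be coarse (Screening and Week 12 only) and are absent from the SAP.

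**The case against.** A 0-or-1 cut is a legitimate responder definition for exploratory efficacy endpoints, and that stands: the endpoints need not be replaced. What is missing is a tolerability summary of the same data.

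Four stronger readings are tempting, and the documents do not support them.

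- *Local worsening goes uncounted altogether.* Moves from 0 or 1 to 2 or 3 lower the planned percentage. Worsening attributed to the drug is an adverse event, tabulated by severity and relationship, and serious events are reportable whatever their cause (Protocol 7.5.7). The gap is complete only for the IAE endpoint.
- *Worsening is an adverse event only if the drug is blamed.* The word only does not appear. The passages say drug-attributed worsening should be recorded (in 7.4.3 and 7.5.6.1, should also be recorded). Section 7.5.6.1 also says any adverse event is reported whether or not related, and requires an open question at each visit. A restrictive reading is plausible but is not the text.
- *The trial would detect the hidden difference with about 88% power.* That needs 225 per arm, and enrolment was discontinued.
- *Phase 2 predicts a scaling problem here.* The signal came from twice-daily dosing in a per-protocol analysis. This trial doses once daily, and the sentence reporting the signal lists no scaling difference for the once-daily arm. Protocol 5.1 describes omiganan as well tolerated, and the most frequent events it lists for the later once-daily study are not skin events.

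It is also fair to say that rewording the adverse-event rule now cannot recover events already left unrecorded, and could mix two recording practices. The table is therefore the main remedy.

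**Conclusion.** The point holds as a gap in the planned summaries. For scaling/peeling and pruritus, 2 of 6 worsening moves cannot change the planned endpoint; for telangiectasia from an eligible baseline, 1 of 3; for erythema from an eligible baseline, 3 of 3. These counts follow from the scales and entry criteria and need no assumed rates. They count kinds of move, not how often each occurs, which the documents do not say.

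The hidden difference of 6 to 12 points is an illustration. It rests on assumed starting grades and worsening rates, and on every worsening stopping at grade 1. No power claim should be attached to it, because the number to be analysed is not stated; at the planned interim size power would be about 36%.

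Whether adverse-event reporting fills the gap depends on how sites read 7.4.2, 7.4.3 and 7.5.6.1, which the documents do not settle. Stopping enrolment and treating all analyses as exploratory does not remove the need to describe tolerability in the subjects treated.

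**What to change.** - **SAP 5.4.4:** add a descriptive table in the all-treated population, by arm, of the number and percent of subjects at least one grade worse than Baseline, at each visit and at the worst post-baseline visit, for IAE, telangiectasia, scaling/peeling and pruritus. Give confidence intervals for the arm differences and no power claim. State the denominators, and keep Week 16 separate from the double-blind period, as SAP 5.4.4 already does for other safety summaries.
- **SAP 5.4.4 or 7.0:** either carry forward the physical-examination shifts from Protocol 7.7.12 or list their removal.
- **Protocol 7.4.2, 7.4.3 and 7.5.6.1:** the attribution wording and the general adverse-event definition must be reconciled. If data collection is complete, the report should state which reading the sites applied.

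Cost: one extra table from data already collected, plus wording changes. The table will include some disease-related worsening in both arms, so it should be read as a comparison between arms and not as a rate of drug-induced irritation. It does not cover burning and dryness, which have no scale and depend on adverse-event reporting.

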## 5.4 Statistical Analysis

### 5.4.1 Subject Accounting, Demographic, and Baseline Characteristics

Demographic, baseline characteristics (including vital signs and laboratory parameters), medical history, and prior and concomitant medications will be summarized by treatment. Study completion status and reasons for discontinuation will also be displayed by treatment.

Previous rosacea therapies taken within the last five years will only be presented in the listings.

### 5.4.2 Efficacy Analysis

The co-primary endpoint of absolute change from baseline in inflammatory lesions will be analyzed using an Analysis of Covariance (ANCOVA) model, with treatment as a main effect, and pooled center as a covariate. To investigate consistency of efficacy results across study centers, treatment by center interaction will be tested at 0.1 level of significance and, if significant, it will be further be explored.

No adjustments will be made for multiple comparisons of efficacy endpoints. All analyses will be considered exploratory in nature due to the discontinuation of enrollment following the interim analysis.

Both IGA endpoints will be analyzed using a Cochran–Mantel–Haenszel (CMH) test, with center as the stratification factor. If the overall IGA response rates are less than 10%, a Fisher’s Exact test will be used to corroborate the CMH test. All tests of the co-primary endpoints will be analyzed.

For all efficacy analyses, small centers may be pooled in order to ensure sufficient cell counts for statistical testing.

Subgroup summaries (e.g. Gender, Age, Race, and Center) of the co-primary endpoints will be performed

[figure not shown]

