
Criteria for Evaluation: Efficacy: Co-Primary endpoints: 1. Absolute change in inflammatory lesion count at week 12; 2. IGA: 2 grade reduction at Week 12; Clear or Almost Clear (IGA of 0 or 1) rating at Week 12. Safety: Adverse events (AE) throughout the study; vital signs at Screening, Week 6 and Week 12; Physical Exam and Safety labs at Screening and Week 12. Immunogenicity will be assessed using samples collected at Baseline, and at Weeks 3, 6, 12 and 16. Statistical Methods: Efficacy: Absolute change in inflammatory lesion count at Week 12 will be analyzed using an Analysis of Covariance, with treatment as a main effect, and center as a covariate. Investigator Global Assessment (IGA) 2 grade reduction at Week 12, and Clear or Almost Clear rating at Week 12 will be analyzed using a Cochran–Mantel–Haenszel (CMH) test, with center as the stratifications factor. An interim analysis for futility will be conducted by an independent statistician. Only absolute lesion reduction count and IGA data (2 grade reduction, and Clear or Almost Clear (0, 1)) will be analyzed in the interim analysis. Safety: AEs will be coded and tabulated by the Medical Dictionary for Regulatory Activities (MedDRA) body system and preferred term, number and percentage of subjects with AEs will be presented. Immunogenicity parameters will be summarized.
	

CONFIDENTIAL

Version Date: 10 July 2015

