7.4.4 Inflammatory Lesion Counts

The area of lesion count assessment is defined as the face from the jaw line to the hairline. The lesion counts will be performed at screening and each study visit (Baseline, Week 1, 3, 6, 9, 12, and 16). The Investigator Global Assessment (IGA), Investigator Assessment of Erythema (IAE) and Other Signs and Symptoms Assessment should be performed prior to performing the lesion count at all visits.

The lesion counts will be performed as follows:

Instructions On Performing Inflammatory Lesion Counts

1. Subjects should have washed their face and removed all makeup at least 15 minutes prior. Male subjects should have already shaved before the study visit.
2. Subjects should be seated at arm's length (or slightly closer) from the evaluator performing the lesion counts and at the same height as the assessor. Subjects should not be seated in direct sunlight.
3. The room should have a balanced and consistent artificial light source or natural light source.
4. The **Principal Investigator or appropriately qualified Sub-Investigators** participating in this study will perform **all** lesion counts. It is essential that the same assessor perform all lesion counts for a given subject for the duration of that subject's participation in the study.
5. Lesions on each area of the face should be considered separately according to the diagram below. Lesions should be counted just to the hairline and no lower than the mandibular line (jaw line). Scan each section of the face systematically from left to right and count only one lesion type at a time. Record each count on the source documents and initial your counts.
6. **ALL LESIONS COUNTED SHOULD BE PALPABLE.** If a lesion is not palpable it should be considered non-active (emerging or resolving). Post-inflammatory lesion pigment changes should not be counted. The inflammatory lesion count includes the total count of papules and pustules, which are defined as follows:

PAPULE – A type of inflammatory lesion; a small erythematous, palpable lesion, usually solid ≤ 0.5 cm in diameter.

[figure not shown]
PUSTULE – A type of inflammatory lesion; a small palpable lesion with an erythematous base approximately 0.5 cm in size and containing pus or yellow-white liquid.

NODULE – A type of inflammatory lesion; a large palpable erythematous papule or plaque that is greater than 0.5 cm in diameter.

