7.7.10 Efficacy Analysis

The co-primary endpoint of absolute change from baseline in inflammatory lesions will be analyzed using an Analysis of Covariance (ANCOVA) model, with treatment as a main effect, and center as a covariate. To investigate consistency of efficacy results across study centers, treatment by study center interaction will be tested at 0.10 level of significance, and if significant, it will be further explored.

The co-primary endpoint of IGA will be tested in the following manner: the 2 grade reduction, and the Clear or Almost Clear (0, 1) will be tested using the Hochberg procedure as follows: Statistical significance will be concluded if both endpoints are significant at a two-sided 0.05 level, or either endpoint is significant at a two-sided 0.025 level. Both IGA endpoints will be analyzed using a Cochran–Mantel–Haenszel (CMH) test, with center as the stratification factor. If the overall IGA response rates are less than 10%, a Fisher's Exact test may be used to corroborate the CMH test. All tests of the co-primary endpoints will be analyzed.

CONFIDENTIAL

Version Date: 10 July 2015

If the co-primary endpoints of absolute lesion reduction and the two IGA endpoints (2 grade reduction, and Clear or Almost Clear (0, 1)) are both significant, the secondary endpoints will be analyzed sequentially in the order listed as follows:

- Test first secondary endpoint at 0.05. If not significant, stop; otherwise,
- Test second secondary endpoint at 0.05. If not significant, stop; otherwise,
- Test third secondary endpoint at 0.05 using Hochberg (similar to the primary method). If not both IGA (0,1) and IGA 2 point reduction are significant, stop; otherwise,
- Test fourth secondary endpoint at 0.05 using the Hochberg method.

For all efficacy analyses, small centers may be pooled in order to ensure sufficient cell counts for statistical testing.

Subgroup analyses (e.g. Gender, Age, Race, and Center) of the co-primary endpoints will be performed.

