### 5.4.3 Interim Analysis

An interim analysis for futility will be conducted by an independent statistician. The purpose of the interim analysis is to help make a decision whether to continue the trial to the planned sample size, or to stop the trial for futility. No increase or decrease to the sample size will be performed, except to stop the trial for futility, therefore no adjustment to type-1 error is indicated. The interim analysis will be based on conditional power analysis when approximately 60 subjects (per group) have completed the study. Only absolute lesion reduction count and IGA data (2 point reduction, and Clear or Almost Clear (0, 1)) will be analyzed following the same statistical approaches as pre-specified in the Efficacy Analysis section.

Conditional power for differences in proportions will be calculated using a Normal approximation, two-sided alpha of 0.05, assuming future data will follow the current trend. The decision rules and algorithm for interim analysis are shown in Figure 1:

Figure 1  
 Graphical Illustration of Interim Analysis Algorithm  
 N=120 (N=60 per group)

The independent unblinded statistician will receive the interim study data and the randomization information confidentially from the CRO. The independent statistician will then follow the algorithm above and make a recommendation accordingly. This

recommendation will be reviewed by designated sponsor's representatives who will make the final decision as to continue the trial as planned or stop for futility. Upon receiving the recommendation, the sponsor may ask the independent statistician to examine additional data before the final decision is made. All communications between the unblinded statistician and the sponsor's representatives will be kept confidential and unknown to all personnel involved in the trial (other sponsor's personnel, CRO, and clinical center personnel). A charter will be written to describe in detail the process and roles related to this interim analysis. This charter will name the independent statistician to conduct the interim analysis, and the sponsor's designated personnel that will make final decisions.

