#### **6.2 Missing Data**

The primary method of dealing with missing data is multiple imputation (MI) technique. All co-primary and secondary endpoints will be analyzed using MI for missing data. As a sensitivity analysis, Observed Case and Baseline Observation Carried Forward (BOCF) will be utilized for the co-primary endpoints only.

The MI technique will be implemented as follows:

a) 100 imputed datasets will be generated to impute missing data using the below SAS code.

1) For inflammatory lesions

```
Proc MI NIMPUTE=100 SEED=20170307  
MIN = . 0 0 0 0 0 0  
MAX = . . . . . . .  
ROUND = . 1 1 1 1 1 1;  
class sex;  
var sex base w1 w3 w6 w9 w12;  
fcs reg(w1) reg(w3) reg(w6) reg(w9) reg(w12);  
run;
```

2) For IGA

```
Proc MI NIMPUTE=100 SEED=20170307  
MIN = . 0 0 0 0 0  
MAX = . 4 4 4 4 4  
ROUND = . 1 1 1 1 1;  
class sex;  
var sex w1 w3 w6 w9 w12;  
fcs reg(w1) reg(w3) reg(w6) reg(w9) reg(w12);  
run;
```

b) The 100 imputed datasets will each be analyzed separately by the methods described in Section 5.4.2.

1) For inflammatory lesions, individual LS means and associated standard errors as well as estimates and standard errors from the pairwise comparison of treatments from the analysis of each imputation will be combined into single estimates, standard errors, and p-value using PROC MIANALYZE as displayed below.

```
Proc MIANALYZE;  
Modeleffects estimate;  
Stderr stderr;  
run;
```

The p-value for the treatment by center interaction will be based on the average of p-values from each the analyses of each imputation.

- 2) For IGA, estimates of the event rates will be based on the average of rates from each imputation. The CMH test statistic from the analysis of each imputation will be converted to a Normal Z score by taking the square root and adjusting for direction (change to a negative value if Omiganan group is worse than Vehicle). These Z scores (with SE=1) will be combined into a single p-value using PROC MIANALYZE as displayed below:

```
Proc MIANALYZE;  
Model effects estimate;  
Stderr SE;  
run;
```

Similarly, the p-values for the one-sided Fisher's Exact test of each imputation will be converted to a Normal Z score using the inverse normal function. These Z scores (with SE=1) will be combined into a single p-value using the same PROC MIANALYZE code.

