## **7.0 Changes from Protocol**

The following changes were made to the analyses planned in the protocol. These changes were due to the discontinuation of enrollment following the interim analysis and subsequent decision to consider all analyses as exploratory in nature.

- The PP population was removed.
- Multiplicity adjustments were removed.

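### The lesion-count ANCOVA leaves out the baseline lesion count; adding it costs one degree of freedom and narrows the interval if change correlates with baseline

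*SAP*

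**What the plan says.** Three places define the lesion-count model. SAP 5.4.2 specifies an "Analysis of Covariance (ANCOVA) model, with treatment as a main effect, and pooled center as a covariate". Protocol 7.7.10 specifies ANCOVA "with treatment as a main effect, and center as a covariate", and the Protocol synopsis specifies "Analysis of Covariance, with treatment as a main effect, and center as a covariate". None of them includes the baseline count.

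The baseline count is available. Protocol 7.4.4 states: "The lesion counts will be performed at screening and each study visit". At least 30 lesions at Baseline is an entry criterion (Protocol 7.2.1). The lesion-count imputation step in SAP 6.2 already uses baseline as a predictor: "var sex base w1 w3 w6 w9 w12".

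No other analysis fills the gap. The observed-case and BOCF sensitivity analyses in SAP 6.2 change only how missing data are handled. SAP 7.0 lists two changes from the protocol: removal of the per-protocol population and of the multiplicity adjustments.

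**The concern.** An ANCOVA of change from baseline would normally include the baseline value. Here the only term besides treatment is center, which is a classification factor. The SAP uses baseline count to predict missing values and then leaves it out of the treatment comparison.

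Validity is not at stake. Randomization makes the unadjusted comparison unbiased, and its type I error is correct. What may be lost is precision: if change correlates with baseline, the interval for the treatment difference is wider than it needs to be. Chance baseline imbalance is the same loss seen conditionally. An imbalance of one standard deviation of the between-arm difference in baseline means shifts the unadjusted estimate by r standard errors.

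Precision is of some interest here because enrollment stopped after the interim analysis. SAP 7.0 records the "decision to consider all analyses as exploratory in nature", so estimates and intervals are the main product.

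**Working it through.** **Inputs.** From SAP 5.1: difference 13.5 − 4 = 9.5 lesions, SD of change 12, power 95%, 43 per group for lesion count and 225 per group overall. From SAP 5.0: two-sided alpha 0.05. From SAP 5.4.3: about 60 per group at the interim. The final number of subjects is not stated, so 60 per group is an illustration. The correlation r, within treatment and center, is given nowhere and is varied from 0 to 0.5. Center degrees of freedom are left out of the figures below; allowing for 7 pooled centers at 60 per group moves a half-width by less than 0.01 lesions.

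**The plan's own figure.** At 43 per group the standard error is 12·√(2/43) = 2.588 and the noncentrality 9.5/2.588 = 3.67. The noncentral t gives power 95.2% at 43 per group and 94.8% at 42, so 43 is reproduced. At 60 per group, power is 99.0%.

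**Effect of adding baseline.**

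- Unadjusted half-width: t(0.975, 2n−2) · 12 · √(2/n). At n = 60: 1.980 · 12 · 0.1826 = 4.34.
- Adjusted half-width: t(0.975, 2n−3) · 12 · √(1−r²) · √(2/n) · √(1 + 1/(2n−4)). The last factor is the expected cost of the extra term. At n = 60 and r = 0.3: 1.980 · 11.45 · 0.1826 · 1.0043 = 4.16.

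| r | Fall in residual variance, r² | Half-width, 60 per group (unadjusted 4.34) | Net change, 60 per group | Half-width, 225 per group (unadjusted 2.22) |
|---|---|---|---|---|
| 0 | 0% | 4.36 | 0.4% wider | 2.23 |
| 0.2 | 4% | 4.27 | 1.6% narrower | 2.18 |
| 0.3 | 9% | 4.16 | 4.2% narrower | 2.12 |
| 0.4 | 16% | 3.99 | 7.9% narrower | 2.04 |
| 0.5 | 25% | 3.77 | 13.0% narrower | 1.93 |

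**Cost and break-even.** If r = 0, variance rises by 1/(2n−4): 1/116 = 0.9% at 60 per group and 1/446 = 0.2% at 225. Break-even is r = √(1/(2n−3)), which is 0.092 and 0.047.

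**Power.** At the design difference of 9.5 lesions and 60 per group, power goes from 99.0% to 99.4% at r = 0.3, so little changes. For an assumed true difference of 5 lesions, a figure not in the documents, power is 61.9% unadjusted. Adjusted, with the cost of the extra term included, it is 63.3, 65.6, 69.1 and 74.0% at r = 0.2, 0.3, 0.4 and 0.5.

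**What the documents hint about r.** Protocol 5.2 reports the first Phase 2 study at Week 9. For all subjects, mean change was −5.93 on omiganan 2.5% QD and −1.50 on vehicle QD. For those with more than 14.5 baseline lesions, "the mean change in lesion count was -7.58 and +0.63 for 2.5% QD and vehicle QD, respectively". From all subjects to the more severe subset, the omiganan mean moves by −7.58 − (−5.93) = −1.65 and the vehicle mean by 0.63 − (−1.50) = +2.13. These are opposite directions, so a pooled slope near zero is possible.

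**Opposite slopes.** A simulation used 20,000 trials of 60 per group with residual SD 12 and slopes in units of 12 lesions per baseline SD. The ratio of adjusted to unadjusted variance was 1.01 for slopes of −0.3 and +0.3 by arm, 1.01 for zero slopes, and 0.92 for a common slope of −0.3.

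**The case against.** The strongest case for leaving the model alone is that nothing in it is wrong and no benefit is documented. No document gives r. The Phase 2 figures compare a whole group with a subset of itself, so they do not estimate a slope, and they point in opposite directions by arm. SAP 1.0 says the efficacy signal grew with baseline count; that suggests effect modification, which a common-slope term does not examine. The entry rule of at least 30 lesions restricts the baseline range and may lower r. The planned total of 450 is set by the IGA endpoint, which this change does not touch. The change would also come after an interim analysis run "following the same statistical approaches as pre-specified in the Efficacy Analysis section", so the final model would differ from the interim one.

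Most of this stands as a limit on the size of the benefit. Two further limits apply. Baseline is already in the imputation model, so adding it to the analysis model does not remove between-imputation variance; with missing Week 12 data, the percentages above are upper bounds. The documents also do not show whether final unblinding has already taken place.

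These points do not reverse the balance. With zero or opposite slopes the cost is about 1% of variance, or 0.02 lesions of half-width at 60 per group. At r between 0.3 and 0.5 the half-width falls by 0.18 to 0.57 lesions. The post-interim problem can be handled by who decides, when, and how the change is labelled.

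**Conclusion.** The point holds as a free improvement. The lesion-count model omits a baseline covariate that is already collected, and no stated analysis adjusts for it. The planned analysis remains valid, and neither its sample size nor its power at the design effect is in question.

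Net of its own cost, the adjustment at 60 per group would narrow the interval by about 2% at r = 0.2 and 13% at r = 0.5, with no gain below r of about 0.09. These figures assume SD 12, a common slope in both arms and complete data. Because r is unknown and may be near zero, the gain is a possibility and cannot be promised.

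**What to change.** In SAP 5.4.2, write the lesion-count model as change = treatment + pooled center + baseline inflammatory lesion count, with baseline continuous. Use it for Weeks 12, 9 and 6 in each of the 100 imputed data sets, and for the Week 12 observed-case and BOCF analyses.

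Decide this before final unblinding, through staff without access to the interim treatment comparison. Record it in SAP 7.0 as a post-interim departure from Protocol 7.7.10 and the synopsis. Keep treatment + pooled center as a labelled sensitivity analysis, so that the result can be compared with the model used at the interim. A treatment-by-baseline term could be examined as support, given the Phase 2 pattern. If final unblinding has already occurred, report the adjusted model only as a post hoc supportive analysis.

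The cost is one model term, one degree of freedom, a text change in SAP 5.4.2, one line in SAP 7.0 and a second run of the lesion-count model. No new data are needed.
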